	
Endpoint 1 (Primary Endpoint): Percentage of subjects without a clinically significant increase in RLS symptoms (i.e. CGI-I score of 5 or less relative to baseline) during the first Phase involving an opioid dose reduction of $\geq 20\%$ relative to baseline.
 
Endpoint 2: Percentage of subjects without a clinically significant increase in RLS symptoms (i.e. CGI-I score of 5 or less relative to baseline) during the first Phase involving an opioid dose reduction of $\geq 1/3$ relative to baseline.
 
Endpoint 3: IRLS during the first Phase with an opioid dose reduction of $\geq 20\%$ relative to baseline.
 
Endpoint 4: IRLS during the first Phase with an opioid dose reduction of $\geq 1/3$ relative to baseline.
 
Endpoint 5: Maximal percentage reduction in opioid dose relative to baseline associated with a CGI-I score of 5 or less, averaged across subjects.
 
Safety
 
Endpoint 1: Frequency of Grade 2 or higher NPNS-related adverse events.
 
Endpoint 2: Frequency of Grade 3 or higher NPNS-related adverse events.
 
Endpoint 3: Percentage of subjects who are discontinued from study due to non-RLS opioid withdrawal symptoms prior to the Extension Phase.
 
NPNS tolerability
 
Percentage of subjects who withdraw from study prior to the Extension Phase citing lack of tolerability of NPNS as the primary reason for withdrawal.
 
Compliance
 
Frequency of device usage on nights with RLS symptoms during Assessment periods during Phase 1 and Phase 2.

Additional Study Assessments (as appropriate)	
 • Weekly assessment of opioid withdrawal symptoms (investigator may employ participant interview and/or COWS scale, as appropriate) • IRLS during run-in week • Nightly subject diary, including RLS symptoms and device usage • Automated compliance tracking – usage data collected via NTX device • Medication use assessment • Subject demographic/characterization assessment • Medication history • Follow-up questionnaire • Leg movement data collected via NTX device

CONFIDENTIAL

All information contained in this document is confidential and is the sole property of Noctrix Health, Inc.
 Any reproduction in part or whole without the written permission of Noctrix Health, Inc. is prohibited.

 NOCTRIX HEALTH	Clinical Trial	Document #: CT-2 (Previously CT-03) Rev: 4.0 (Superseded Rev C) CC#: 720 (Previously DCO #138) Effective: 09/24/2021

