17.4. Compliance

Compliance will be measured based on digital tracking of the timing and duration of each NPNS device usage during the Assessment weeks of Phase 1 and Phase 2. A “*night of compliant use*” will be defined as a minimum of 25 minutes of active NPNS stimulation between 5pm and 8am during an Assessment week. “*Total assessment nights*” will be defined as the total nights spent by all subjects in Assessment weeks. “*Total assessment nights with RLS symptoms*” will be defined as the total nights spent by all subjects in Assessment weeks when the subject reports RLS symptoms on the Daily questionnaire. If a subject is removed from the study before the end of an Assessment week, such as due to an adverse event or for personal reasons, data from that Assessment week will not be included in the compliance analysis. In cases where digital tracking logs are incomplete or unavailable, the data will not be included in the compliance analysis.

- For participants who are instructed to administer stimulation each night, percentage compliance will be calculated using the following formula:
 - $100\% * (\text{nights of compliant use}) / (\text{total assessment nights})$
- For participants who are instructed to administer stimulation only on nights with RLS symptoms, percentage compliance will be calculated using the following formula:
 - $100\% * (\text{nights of compliant use}) / (\text{total assessment nights with RLS symptoms})$

The global criterion for success will be percentage compliance of $\geq 70\%$, based on the weighted average of individual compliances (i.e. weighting nights equally instead of weighting participants equally).

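### The compliance analysis drops the Assessment week of anyone removed before it ends, and any data with incomplete logs, so it may overstate compliance against the 70% criterion

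*Combined protocol and SAP*

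**What the plan says.** Section 17.4 defines a compliant night as "a minimum of 25 minutes of active NPNS stimulation between 5pm and 8am during an Assessment week", taken from digital tracking. The denominator starts as "the total nights spent by all subjects in Assessment weeks". For subjects told to stimulate only when symptomatic, it is restricted to nights with reported RLS symptoms. The success criterion is at least 70%, calculated by "weighting nights equally instead of weighting participants equally".

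Two exclusions come before that calculation:

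- **Early removal.** "If a subject is removed from the study before the end of an Assessment week", for which the plan gives an adverse event and personal reasons as examples, "data from that Assessment week will not be included in the compliance analysis".
- **Log loss.** "In cases where digital tracking logs are incomplete or unavailable, the data will not be included in the compliance analysis". The text does not say whether the unit dropped is the night, the week or the subject, and does not distinguish causes.

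Section 17.4 sets no limit on excluded data, does not ask for a count of excluded nights, and plans no sensitivity analysis. Section 16.12 lists the grounds for removing a subject. They include persistent non-compliance, an adverse event that prevents further participation, and a reduced opioid dose that is not tolerable. Section 16.9 says that the devices log usage automatically throughout the study.

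**The concern.** Under the early-removal rule, whether a night is analysed can depend on the quantity being measured. A subject who stops using the device during an Assessment week may be removed for persistent non-compliance, and the week that shows the low use then leaves both numerator and denominator. A subject who uses the device less because of an adverse event and then exits is treated the same way. The nights before removal should already be in the device log, so the rule discards data that exist.

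The plan handles early exit differently elsewhere. Under sections 13.2 and 17.1.3, subjects who leave during run-in because of intolerable RLS symptoms still count in the efficacy endpoint. Under section 17.3, the tolerability criterion uses everyone who begins stimulation as its denominator. Compliance has no comparable protection.

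What is at stake is the pass or fail on the 70% criterion. It is a bare point estimate with no interval around it, so a modest number of selectively missing nights could decide it.

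**Working it through.** **Plan figure.** The 70% is a chosen cut-off. The documents give no derivation, sample size or test for it, so there is nothing to reproduce.

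**Inputs from the documents.** Threshold 70%, with nights weighted equally (section 17.4). Enrolment of 20 to 40 in the primary study (Synopsis). Two one-week Assessment periods, nominally 14 nights per subject, so at most about 20 × 14 = 280 to 40 × 14 = 560 nights.

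**Inputs assumed.** The share of all nights that is dropped (f) and the compliance on those nights (c). The documents give neither.

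**Step 1: can low use cause exclusion?** For early removal, yes. Section 16.12 permits removal for persistent non-compliance, and section 17.4 then deletes the week. For log loss, the documents describe no such path, and the cause may be purely technical.

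**Step 2: effect on the percentage.** With observed compliance p on retained nights:

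all-night compliance = (1 − f) × p + f × c

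This falls below 70% once f exceeds (p − 0.70) / (p − c).

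| Compliance on dropped nights (c) | Limit on f if p = 75% | Limit on f if p = 80% |
|---|---|---|
| 0% | 0.05/0.75 = 6.7% | 0.10/0.80 = 12.5% |
| 25% | 0.05/0.50 = 10.0% | 0.10/0.55 = 18.2% |
| 50% | 0.05/0.25 = 20.0% | 0.10/0.30 = 33.3% |

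**Step 3: observed rate needed.** With c = 0, all-night compliance of 70% requires an observed rate of 70% / (1 − f):

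- f = 5%: 73.7%
- f = 10%: 77.8%
- f = 15%: 82.4%
- f = 20%: 87.5%

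**Step 4: no bias, or bias the other way.** If c = p, the formula returns p, so nothing changes. If dropped nights are fully compliant, the rule understates compliance. With p = 75% and f = 10%, 0.90 × 75% + 10% = 77.5%.

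**Step 5: two worked cases, all counts assumed.**

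- *Result sensitive to the rule.* Of 20 subjects, 16 complete both weeks: 16 × 14 = 224 nights, 168 compliant, 75.0%. Four others are removed during the Phase 1 Assessment week with no compliant nights. With 4 nights each before removal, the rate is 168/(224 + 16) = 168/240 = 70.0%, exactly at the threshold. With 6 nights each, it is 168/(224 + 24) = 168/248 = 67.7%, a fail.
- *Result not sensitive.* Of 20 subjects, 18 complete both weeks: 252 nights at 72%, or 181.4 compliant. Two are removed with 7 logged nights between them, none compliant. Then f = 7/259 = 2.7% and the rate is 181.4/259 = 70.1%, still a pass.

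**The case against.** The best defence is that neither direction nor size is established.

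- An adverse event need not mean low use, because section 17.2.2 also counts events related to opioid withdrawal.
- A subject leaving with worsening RLS may use the device more, since section 16.7 ties use to symptoms and allows up to four sessions a day.
- Section 16.10 says that exit typically occurs at the end of a phase, and run-in nights never count, so few nights may be lost to early removal.
- Device intolerance is visible elsewhere: it has its own criterion in section 17.3 and its own endpoints in section 17.2.1.

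Most of this stands as a limit on the claim. It does not restore the deleted nights or remove the route from persistent non-compliance to exclusion.

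Three stronger readings are tempting, and the documents do not support them:

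- *The criterion is judged only on the subjects most likely to comply.* The text drops weeks or data, not people. A subject removed in the Phase 2 Assessment week keeps a completed Phase 1 week.
- *Missing logs also inflate the result.* Nothing links log loss to low use.
- *The diary already holds what is discarded.* The Synopsis lists a "Nightly subject diary, including RLS symptoms and device usage", but nothing shows that it records the minutes and clock times that the definition of a compliant night needs. Self-report in the main analysis would also mix two measures and could itself raise the percentage.

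**Conclusion.** The point holds in limited form. The early-removal rule can exclude nights because of low use and so may overstate compliance. That direction is a reasonable inference from sections 16.12 and 17.4 read together; the plan does not state it. For missing logs the direction is uncertain, and the firmer defect is that the unit of exclusion is undefined.

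The size cannot be computed from the documents. If every dropped night is non-compliant, the pass is lost above 6.7% of nights dropped for an observed 75%, and above 12.5% for an observed 80%. These limits widen as dropped nights become more compliant, and the bias disappears when they match retained nights. A reader might infer that the criterion would be missed, but that follows only from particular choices of f, c and the observed rate.

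This is a low-cost improvement to a secondary criterion in an exploratory single-arm study. Compliance does not enter the primary endpoint.

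**What to change.** Amend section 17.4 as follows:

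1. In the main compliance analysis, include all logged nights up to the time of removal, in both numerator and denominator.
2. For missing logs, exclude only the individual nights without a usable log, and state that the night is the unit.
3. Report the number of nights excluded and the reason for each exclusion.
4. Add a sensitivity analysis of the 70% criterion that counts excluded nights as non-compliant.
5. Use diary-reported device usage, if at all, only as a further sensitivity analysis, with a stated rule for relating it to the 25-minute, 5pm to 8am definition.

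The cost is slightly more analysis, on data that the devices are already set to log, and a compliance figure that may be less favourable.

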5.2.2. Dosage and dosage regimen

The dosage depends on the intensity and duration of stimulation:

1. Setpoint stimulation intensity. The setpoint stimulation intensity will be the lesser of (a) the maximal intensity that the subject reports is non-distracting and comfortable, as determined in the calibration session described in the instructions for device use and (b) the maximal intensity for each set of stimulation parameters, as determined based on device output capabilities.
2. Participants will be allowed to adjust stimulation intensity from the setpoint, but only within a limited pre-programmed range. For example, participant may increase intensity if symptoms are severe or reduce intensity if symptoms are mild.
3. Participants may be instructed to administer stimulation each night or only administer stimulation when RLS symptoms are present.
4. Stimulation may be activated for up to 120 minutes per day, depending on the timing, duration, and severity of RLS symptoms for the specific subject.

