16.7. Study Treatment Description

Study subjects are instructed to self-administer treatment for at least 30 minutes on each night that they experience RLS symptoms. Study subjects may self-administer up to four 30-min sessions per day, as needed based on RLS symptoms. The instructions for timing of these "as needed" doses will be determined at the discretion of the investigator and research staff, based on the RLS symptoms experienced by the subject.

CONFIDENTIAL

 NOCTRIX HEALTH	Clinical Trial Investigational Plan, Protocol CT-03 (Opioid Reduction Study)	Document #: CT-2 (Previously CT-03) Rev: 4.0 (Superseded Rev C) CC#: 720 (Previously DCO #138) Effective: 09/24/2021
---	---	---

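### The 70% compliance criterion in Section 17.4 does not measure the synopsis endpoint for nightly-instructed subjects, and its numerator and night weighting need defining

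*Combined protocol and SAP*

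**What the plan says.** The synopsis lists a single compliance endpoint with no split by instruction: "Frequency of device usage on nights with RLS symptoms during Assessment periods during Phase 1 and Phase 2".

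Section 5.2.2 allows two instructions: "Participants may be instructed to administer stimulation each night or only administer stimulation when RLS symptoms are present". Section 16.7 gives only one: "Study subjects are instructed to self-administer treatment for at least 30 minutes on each night that they experience RLS symptoms". Section 13.2 lets the investigator adjust the instructed schedule of device use during a step-down.

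Section 17.4 turns compliance into numbers, as follows.

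- **Numerator.** A compliant night is "a minimum of 25 minutes of active NPNS stimulation between 5pm and 8am during an Assessment week". It need not be a night with symptoms.
- **Denominator, nightly instruction.** "For participants who are instructed to administer stimulation each night, percentage compliance will be calculated using the following formula": compliant nights over total assessment nights.
- **Denominator, symptom-night instruction.** "For participants who are instructed to administer stimulation only on nights with RLS symptoms, percentage compliance will be calculated using the following formula": compliant nights over assessment nights on which the subject reported symptoms in the Daily questionnaire.
- **Success.** "The global criterion for success will be percentage compliance of" at least 70%, as a weighted average of individual compliances, explained as "weighting nights equally instead of weighting participants equally".

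**The concern.** The synopsis and Section 17.4 use different denominators for anyone told to stimulate every night. The pass/fail rule therefore combines two quantities: use on symptom nights for some subjects and use on all nights for others. Only the first is the declared endpoint.

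Two features of Section 17.4 add to this. Under the symptom-night formula the numerator can include nights that are absent from the denominator, so an individual score can exceed 100% and offset non-use elsewhere. And the weighting phrase does not say whether the weights are Assessment nights or the nights in each subject's own denominator. These give different results once the denominators differ between subjects.

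At stake is whether a prespecified success criterion can be read in only one way, and whether meeting it supports a statement about the endpoint in the synopsis.

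**Working it through.** **Inputs from the documents.** One Assessment week per Phase, so 7 nights (Section 13.2); the two formulas and the 70% threshold (Section 17.4); 20 to 40 subjects in the primary study (synopsis). The threshold has no derivation to reproduce.

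**Assumptions.** The documents give neither the number of symptom nights per week nor the share of nightly-instructed subjects. Call these s and f. Steps 1 and 2 assume that every subject has s symptom nights of 7 and uses the device on exactly those nights.

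**Step 1, one subject.** The synopsis measure is s/s = 100% throughout. The nightly formula gives s/7:

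| s | 1 | 2 | 3 | 4 | 5 | 6 | 7 |
|---|---|---|---|---|---|---|---|
| Nightly formula, % | 14.3 | 28.6 | 42.9 | 57.1 | 71.4 | 85.7 | 100 |

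The score is below 70% only when s is 4 or fewer.

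**Step 2, the global figure.** There are two readings of the weighting.

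- Reading A weights each individual compliance by Assessment nights (7 each): f·(s/7) + (1 − f)·1. It falls below 0.70 when f > 0.30/(1 − s/7).
- Reading B divides pooled numerators by pooled denominators: s/[7f + s(1 − f)]. It falls below 0.70 when f > (s/0.7 − s)/(7 − s).

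| s | Fails under A if f exceeds | Fails under B if f exceeds |
|---|---|---|
| 1 | 35.0% | 7.1% |
| 2 | 42.0% | 17.1% |
| 3 | 52.5% | 32.1% |
| 4 | 70.0% | 57.1% |
| 5 or more | never | never |

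Example with s = 3 and 30 subjects, 15 under each instruction:

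- Reading A: (15 × 42.9% + 15 × 100%)/30 = 71.4%, a pass.
- Reading B: (15 × 3 + 15 × 3)/(15 × 7 + 15 × 3) = 90/150 = 60%, a fail.
- Synopsis measure: 90/90 = 100%.

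**Step 3, the opposite direction.** A nightly-instructed subject has 3 symptom nights and uses the device on 4 symptom-free nights and 1 symptom night. Section 17.4 gives 5/7 = 71.4%; the synopsis measure is 1/3 = 33.3%.

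**Step 4, the numerator.** A symptom-night-instructed subject with 3 symptom nights uses the device on all 7 nights and scores 7/3 = 233%. Add two subjects under the same instruction, each with 3 symptom nights and no use.

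- Reading A: (233.3% + 0 + 0)/3 = 77.8%.
- Reading B: 7/(3 + 3 + 3) = 77.8%.
- Synopsis measure: 3/9 = 33.3%.

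The criterion is met under either reading although two of the three subjects never used the device.

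**The case against.** The best defence is that Section 17.4 is the only operational definition of compliance and that it measures adherence sensibly. Section 5.2.2 permits two instructions, and each subject is scored against the one received. Someone told to stimulate nightly who does so on 3 nights of 7 did not follow the instruction, and 43% is a coherent description of that. This stands: the nightly formula is not wrong in itself. It does not, however, make the formula a measure of the synopsis endpoint.

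The mismatch could also be removed by rewriting the synopsis to match Section 17.4. That would settle the declaration, but the mixed denominators, the unmatched numerator and the open weighting would remain.

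Four stronger readings are tempting and are not supported.

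- **That Section 16.7 also defines compliance.** It is a treatment instruction. Only the synopsis conflicts with Section 17.4 on the endpoint; Section 16.7 differs from Section 5.2.2 on the instruction.
- **That the choice of denominator will flip the result.** One subject's 43% cannot flip a global criterion. The flip needs 4 or fewer symptom nights (under exact use on those nights) and enough nightly-instructed subjects.
- **That nightly-instructed subjects necessarily carry more weight.** This is true under Reading B but not under Reading A.
- **That the instruction goes unrecorded.** Table 5A has no row for it, but that table is a schedule of assessments and the case report forms are not in the documents. The run-in is also meant to settle the usage instructions before the Assessment week.

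**Conclusion.** The point holds as a definitional fault in a secondary success criterion. The synopsis and Section 17.4 state different denominators for nightly-instructed subjects, and the 70% rule combines both kinds. The uncapped numerator and the unspecified weights are faults within Section 17.4 itself and do not depend on the mismatch.

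The size cannot be fixed from the documents. Under exact use on symptom nights, a nightly-instructed subject scores between 14% and 100% where the synopsis measure is 100%. At s = 3 the global criterion fails once the nightly-instructed share exceeds about 32% (Reading B) or 52.5% (Reading A); at s = 5 or more it does not fail at any share. The figures in Steps 3 and 4 are illustrations of what the formulas allow, not forecasts.

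The consequence is limited. Compliance is not the primary endpoint, the study is titled exploratory, and no efficacy or safety criterion is affected. The point is a minor one, worth settling because the correction is cheap.

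**What to change.** 1. Apply the 70% criterion to the declared endpoint for every subject: symptom nights with at least 25 minutes of active stimulation in the existing time window, divided by symptom nights, both summed over subjects. This cannot exceed 100%.
2. State the weighting outright: each symptom night counts once. This keeps the plan's preference for weighting nights rather than participants.
3. Report adherence to the instruction given as a second line, with all-night use for nightly-instructed subjects, and give the number of subjects under each instruction.
4. Note the instruction in force at the start of each Assessment week, if the case report form does not already do so.
5. Reconcile Sections 5.2.2, 16.7 and 17.4 on the stimulation instruction. No view is taken here on which instruction is right.

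**Cost.** The device logs and the Daily questionnaire already supply the data, so at most one extra field is needed. Section 17.4 is protocol text, so the change needs IRB approval under Section 10.5. Nightly-instructed subjects with no symptom nights would count only in the second line.

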17.5. Exploratory Analysis

Additional statistical analysis that is exploratory in nature may be performed, which may include but is not limited to analysis of data from the Extension Phase.

18. Remote procedures

CONFIDENTIAL

All information contained in this document is confidential and is the sole property of Noctrix Health, Inc.

Any reproduction in part or whole without the written permission of Noctrix Health, Inc. is prohibited.

 NOCTRIX HEALTH	Clinical Trial Investigational Plan, Protocol CT-03 (Opioid Reduction Study)	Document #: CT-2 (Previously CT-03) Rev: 4.0 (Superseded Rev C) CC#: 720 (Previously DCO #138) Effective: 09/24/2021
---	---	---

During and after the COVID-19 pandemic, replacing some in-person visits with remote interactions may be necessary, for example to reduce risk to subjects and/or to comply with local, state, or federal regulations. In such cases, the study records will indicate which in-person visits were replaced with remote interactions. The allowable study duration may be expanded as needed to allow delay intervals for mailing and receiving programmed devices.

In such cases, one of more of the following approaches may be taken:

1. Remote calibration and training. Remote calibration and training, where possible, will be coordinated by mailing a calibration/training device to the subject, conducting calibration and training via a video call using the calibration/training device, and then mailing programmed devices to the subject using the settings determined during the calibration. Alternatively, the same devices used in the study may be used for calibration/training.
2. Remote follow-up visits. Remote follow-up visits, where possible, will be completed via call or video call, during which the required study assessments will be administered.
3. Devices may be returned using a pre-paid mailing label, as needed.
4. Remote consent. Remote consent procedures will follow the recommendations set forth in the “FDA Guidance on Conduct of Clinical Trials of Medical Products during COVID-19 Public Health Emergency” [12]. For example, or more of the following procedures listed in the guidance will be used to confirm consent:
 - a. eConsent via a compliant digital platform;
 - b. confirmation of consent by an impartial witness via three-way call or video conference;
 - c. remote explanation of consent followed by in-person signature of informed consent document (to minimize duration of in-person interaction).

19. References

